Design Overview. This study will be completed as a 6-day inpatient protocol on the Johns Hopkins Hospital and/or Bayview Clinical Research Units (CRU). The sequence and timing of study procedures is shown below. Male (accrual n=12) and female (accrual n=12) participants will be randomized to receive intranasal OT (40 IU/dose) or placebo three times daily. During the CRU stay, participants will complete self-report assessments of alcohol craving, anxiety and depression; nursing staff will administer the CIWA-Ar to evaluate withdrawal symptom severity. Full descriptions for OT administration and assessment instruments are below. During the first 3 days, participants will undergo alcohol abstinence during which 24-hr urinary free cortisol (UFC) will be collected for the first 48 hours. Participants will then complete 3 laboratory procedures in fixed order. A urine toxicology screen, a breath alcohol test, and urine pregnancy test (women) are completed prior to all procedures. Subjects will be terminated from this protocol if they have positive drug toxicology tests (excluding THC) or a positive pregnancy test (females). On procedure days, subjects receive a calorie-controlled breakfast and lunch to control for dietary effects on alcohol absorption or stress response. On day 4, a Trier Social Stress Test (TSST), which includes performance of mental arithmetic and public speaking, will be used to examine subjective and physiological responses to stress. On day 5, an Alcohol Motivated Responding (AMR) procedure, in which subjects respond on the computer to earn either drinks or money and then have the opportunity to self-administer earned drinks, will be used to determine OT effects on motivation to drink and alcohol self-administration. On day 6, a Cumulative Alcohol Dosing (CAD) procedure will be used to examine physiological and subjective responses to fixed-dose alcohol administration. The TSST, AMR and CAD laboratory sessions will start at 1 pm, 30 min after the mid-day OT or placebo administration since OT reaches peak levels in plasma 30-40 min after intranasal administration^[76-78]. On day 7, subjects will have a brief intervention for their hazardous drinking before discharge.

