Subjects who smoke cigarettes or other tobacco products will not be allowed to smoke at any time during the JHH CRU stay. Current smokers on the JHH CRU will be provided with a transdermal nicotine patch (21 mg) at admission and each morning to prevent the onset of nicotine withdrawal; smokers will be patched throughout their JHH CRU stay. Participants residing on the Bayview CRU will be allowed to smoke ad lib in the designated smoking room in the facility. Cigarettes will be held at the nursing station to prevent unauthorized smoking in the participant's bedroom. They will have the option to receive a transdermal patch (21 mg) on the days that they are transported to the JHH campus to complete study procedures.

All session procedures (TSST, ARM and CAD) will be completed in our research office (550 Building). Subjects staying at the JHH CRU will transfer to the Bayview CRU after the TSST for

the remainder of the study. Subjects will be transported via car service to the 550 Building for sessions, then return to the Bayview CRU. The sequence of conditions is:

- Day 1: Admission to Bayview CRU (or JHH CRU)*
** Subjects will be only be admitted to JHH Bayview if they meet defined parameters (see definition below)*
- Days 1-6: Intranasal self-administration of OT (40IU/dose) or placebo three times daily under nursing supervision.
Completion of daily self-report measures three times daily
- Days 1 - 2: Monitored alcohol abstinence
Staff administered CIWA-Ar every four hours while awake*
24-hr collection of urinary free cortisol
Practice AMR session procedures
** symptom triggered benzodiazepine treatment (see below)*
- Day 4: Session 1: Trier social stress test (TSST)
** JHH CRU participants transfer to the Bayview CRU (after TSST session) for the remainder of the study*
- Day 5: Session 2: Alcohol motivated responding (ARM) procedure
- Day 6: Session 3: Cumulative alcohol dosing (CAD) procedure
- Day 7: Brief Intervention for heavy drinking and CRU discharge

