Urinary free cortisol measurement. All subjects will provide urine samples for urinary free CORT (UFC), as a measure of withdrawal-related stress response. During the CRU stay, all urine voided per 24-hrs for the first 48 hours is collected in containers containing boric acid as a preservative as in our previous study^[19]; an aliquot is frozen (-70°C) for analysis of UFC via Liquid Chromatography, Tandem Mass Spectrometry (LC/MS/MS) by Quest Diagnostics Nichols Inst. San Juan Capistrano. The coefficient of variance is 5% and 7% for the intra-assay and the inter-assay, respectively.

Oxytocin (OT) administration. OT (syntocinon, Novartis) 40 IU/ml, Pharmaworld, Zurich, Switzerland) and placebo (generic saline nasal spray, various vendors) will be transferred by JHH IDS in identical sterile metered-dose nasal spray bottles (Lukas-Bottles, 6-ml) to deliver 0.1 mL/spray. Pharmaworld has provided oxytocin for numerous clinical trials in the US, including prior studies by [name] (Co-I). Syntocinon previously was an FDA-approved product (NDA 012285) used medically for labor induction, but was discontinued. It is no longer marketed by Novartis. Oxytocin will be used in these studies under FDA-approval via IND 110,562, which held by our collaborator [name].

Johns Hopkins Hospital Investigational Drug Services will maintain and dispense spray bottles per study randomization schedule. Subjects will self-administer 5 sprays per nostril, 30s apart, of placebo or OT (4 IU/spray x 10 sprays = 40IU total dose) 3-times/day under nurse supervision (e.g., 7 am, 12:30 pm, 7 pm).

Daily self-report measures. The CRU nurses and research staff will insure completion of self-report instruments for alcohol craving (visual analog scale, VAS^[83]; Alcohol Urges Questionnaire^[84]), POMS short^[85, 86] and medication side effects using a modified version of the SAFTEE^[87]. Alcohol craving, a new diagnostic criterion for AUD in the DSM-V, is a primary trigger for relapse.

Reductions in craving are strongly associated with better treatment outcomes for behavioral interventions and AUD medications^[88-90].

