Ethyl Alcohol/Alcohol: Alcoholic beverages are legally sold to adults. The dose of alcohol used in the CAD was selected to bring blood ethanol levels to approximately 0.1% was determined based on our previous studies and a comprehensive literature on administering alcohol to research subjects. This BAC corresponds to about 1 g/kg alcohol. The drink is prepared by IDS using 190 Proof ethanol (95%v/v, 0.775 g/ml Spectrum Chemical); the total alcohol dose is divided over three drinks, prepared by mixing the appropriate amount of pure ethanol with a sweet beverage. Using standardized drinking units, 1 (e.g. (One standard drink is equivalent to 12 ounces of beer, 5 ounces of wine, or 1.5 ounces of 80-proof spirits.), this amount is about 4-5 drinks for men and about 3-4 drinks for women when consumed in over 2-hour drinking episode. This amount is within the limits of the typical drinking episode of participants, and are not expected to produce significant adverse events.

After the AMR, subjects may consume up to up to 5 standard drinks (70g ethyl alcohol) of an alcoholic beverage of their choice (e.g., beer, wine or liquor) during the alcohol self-administration session, and drinking is paced. These amounts are within the limits of the typical drinking episode of participants and also are sufficiently large to promote alcohol-motivated responding.

Use of intranasal OT and alcohol will be under FDA-approval via IND 110,562 (holder [name], Co-I, *amendment submitted to FDA 8/4/14*). Amendment application is uploaded to eIRB protocol.

Nicotine Patch: Active nicotine patch (21 mg) is the standard of care for management of nicotine withdrawal.

b. Justification and safety information if FDA approved drugs will be administered for non-FDA approved indications or if doses or routes of administration or participant populations are changed.

n/a

c. Justification and safety information if non-FDA approved drugs without an IND will be administered.

n/a/

7. Study Statistics

a. Primary Outcome variables:

- Peak scores for CIWA-Ar and Craving Scales for abstinence days 1-3.
- Total and subscale scores on POMs Short at assessment and during the CRU stay
- UFC for abstinence days 1-3
- Peak salivary CORT in the TSST
- Number of drinks earned in the AMR
- Peak drug effect VAS scores and peak increase in heart beats per minute (bpm) in the CAD

b. Secondary Outcome variables:

- Stimulation and sedation subscales of the BAES in the CAD

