- Total score of the SHAS in the CAD
- Total scores for the tension and anxiety subscale of the POMS at assessment, during the TSST, and during withdrawal
- Side effects reported on the SAFTEE during the CRU stay

c. Statistical plan including sample size justification and interim data analysis:

In AUD treatment research, a moderate effect of 30-40% improvement is typical. The primary objective of this protocol is to generate estimates of effect size and variance between the OT and placebo treatment groups that could be used to calculate sample size for a larger scale, Phase III study. We have effect sizes for some of our variables using data drawn from the literature and our prior studies. For our power analyses we set type I error (α) = 0.05 where power ($1-\beta$) = 0.8 for the specified effect size for each outcome measure between the OT and placebo treatment groups (n=12 per group, 24 total). Data from prior small trial^[56] showed the OT group (n=7) had 3-fold lower CIWA-Ar scores and a 40% decrease in craving vs. the placebo group (n=4) on day 1. In our prior study in AUD subjects (n=25)^[117], the mean (SD) peak alcohol craving on day 1 of abstinence was 23.4 (7.9). We have power (0.89) to detect a 40% difference in CIWA-Ar and craving between treatment groups (Aim 1). In a previous study, OT reduced stress-induced salivary CORT by 30%^[38]. Based on our TSST data (n=414), with mean (SD) peak salivary CORT of 0.48 (0.46), we will have power (0.8) to detect a 30% difference in CORT between treatment groups (Aim 2). In our pilot study (n=9), subjects drank an average of 3.1 (1.9 SD) drinks, although the 3 drinkers most similar to those in the proposed study drank a

mean of 5 drinks (2.7 SD). We have power (>0.8) to detect a 30% difference in drinks between groups (Aim 3). In our preliminary data ($n=101$), mean (SD) was 118 (62.8) for VAS scores and +13(6.6) for bpm. We have power >0.8 to detect a 40% reduction in peak VAS and bpm (Aim 4). Thus, our sample size of 24 subjects should be sufficient to detect differences between treatment groups, assuming a moderate effect of OT.

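### The Aim 1 peak outcome is not anchored to the first dose, so any day-1 rating taken before treatment counts toward it and would pull the estimated effect toward zero

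*Protocol*

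**What the plan says.** Section 7.a lists, among the primary outcomes, "Peak scores for CIWA-Ar and Craving Scales for abstinence days 1-3". Section 4.a sets the clock for that window:

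- The Design Overview says "During the first 3 days, participants will undergo alcohol abstinence".
- The sequence of conditions begins with "Day 1: Admission to Bayview CRU (or JHH CRU", so abstinence day 1 is the admission day.
- Study drug starts on the same day: "Days 1-6: Intranasal self-administration of OT (40IU/dose) or placebo three times daily under nursing supervision".
- Craving is rated under the same item: "Completion of daily self-report measures three times daily".
- Withdrawal is rated on its own cycle: "Staff administered CIWA-Ar every four hours while awake".
- Dosing times are given only as examples: "3-times/day under nurse supervision (e.g., 7 am, 12:30 pm, 7 pm". They are not tied to the hour of admission or to any rating.

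The statistical plan (7.c) takes its craving planning value from the first day: "the mean (SD) peak alcohol craving on day 1 of abstinence was 23.4 (7.9". The prior trial it cites for a 40% lower craving score also reports day 1. Section 7.c plans t-tests and an ANCOVA. Its example covariates are gender and mean drinks per week; a pre-dose score is not among them.

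**The concern.** The window opens at admission, but treatment opens at the first dose, and the protocol does not say how far apart the two are. A CIWA-Ar or craving score taken in between cannot be affected by oxytocin, yet the definition admits it.

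The choice of a maximum makes this matter. In an average over three days, one early score would be diluted. In a maximum, one score can decide the result. If oxytocin lowers later scores, the recorded peak still cannot fall below the pre-dose score. The same floor exists under placebo, but it binds less often there because later scores are higher. The bias therefore runs toward no difference.

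Two things are at stake. One is the test of Hypothesis 1a. The other, which the protocol puts first in 7.c, is the estimate of effect size and variance for planning a larger trial. A diluted estimate would carry into that sample size.

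**Working it through.** **Inputs from the protocol (7.c).** Peak craving 23.4, SD 7.9; effect 40%; 12 per group; α = 0.05 with sidedness not stated; stated power 0.89; two-sample t-test.

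**Step 1: the plan's own figure.** Difference = 0.4 × 23.4 = 9.36. Standardised difference = 9.36 / 7.9 = 1.18. With 12 per group:

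- One-sided α 0.05: power 0.878 (t) or 0.896 (normal approximation). This matches the stated 0.89.
- Two-sided α 0.05: power 0.792 (t) or 0.827 (normal).

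The two-sided t value, 0.79, is the reference below. No CIWA-Ar mean or SD is given, so only craving can be checked.

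**Step 2: the mechanism, without variability.** Let the pre-dose score be a fraction f of the untreated peak. A true 40% reduction puts the treated post-dose peak at 0.6 × 23.4 = 14.04. The recorded treated peak is max(f, 0.6) × 23.4, so the recorded reduction is 1 − max(f, 0.6):

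- f ≤ 0.6: 40%, no loss
- f = 0.7: 30%
- f = 0.8: 20%
- f = 0.9: 10%

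**Step 3: with variability.** Simulation of 40,000 trials with 12 per arm. The post-dose peak has mean 23.4 under placebo and 14.04 under oxytocin, SD 7.9 in each arm, truncated at zero. The recorded outcome is max(pre-dose, post-dose).

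Assumptions that the protocol does not supply: every participant has one pre-dose score; its mean is the stated fraction of 23.4 and its SD the same fraction of 7.9; its correlation with the post-dose peak is 0.5 or 0.8; and 23.4 (7.9), a day-1 figure, stands for the peak over days 1-3. Ranges cover the two correlations.

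| Pre-dose mean, as share of untreated later peak | Peak is pre-dose: placebo | Peak is pre-dose: oxytocin | Mean difference | Two-sided power |
|---|---|---|---|---|
| no pre-dose score | – | – | about 9.2 | 0.79 |
| 25% | under 1% | 10–13% | 8.9–9.0 | 0.79 |
| 50% | 1–4% | 33–37% | 7.8–8.2 | 0.73–0.76 |
| 75% | 11–21% | 69–77% | 5.2–5.5 | 0.45–0.46 |
| 100% | 50% | 88–97% | 1.9–2.7 | 0.08–0.14 |

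The first row shows 9.2 rather than 9.36 because of the truncation at zero. The share of the difference retained is 7.8/9.2 to 8.2/9.2 = 85–89% at the 50% level, 5.2/9.2 to 5.5/9.2 = 57–60% at 75%, and 1.9/9.2 to 2.7/9.2 = 21–29% at 100%.

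If only some participants have a pre-dose score, the result lies between the relevant row and 0.79. A pre-dose SD as large as the full 7.9 would lower the 50% and 75% rows further.

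**The case against.** The strongest reply is that the protocol nowhere says a rating is taken before dose 1. Dosing starts on day 1, self-reports share a line with dosing, and the dosing times are only examples. If all three doses fall on the admission day, the first comes early and leaves little room for an earlier rating. This stands, and it is why the loss is stated as conditional. It does not remove the point. CIWA-Ar runs on a four-hour cycle that is independent of dosing, admission can fall between dosing times, and no rule keeps an early score out of the peak.

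A second reply is that rules for analysis windows usually belong in the statistical analysis plan, which is not at hand. Here, however, section 7.a itself fixes the window. A later plan would have to narrow what the protocol states.

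A reader might infer more than the text supports:

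- *That the definition will hide a real effect.* The loss is negligible at the 25% level, small at 50% and large only from about three quarters upward. The protocol gives no pre-dose level.
- *That the floor lies under the oxytocin arm alone.* It enters both arms and binds mostly in the oxytocin arm. It does not inflate type I error.
- *That no baseline exists.* CIWA-Ar is given at the assessment visit. Only craving has no dedicated scale in Table 1.
- *That re-anchoring would lift power to 0.94–0.97.* Such values need smaller SDs than the protocol's 7.9.

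**Conclusion.** The outcome window is unanchored, and that is a real weakness of the definition in 7.a. Followed as written, any rating before dose 1 counts, cannot respond to treatment, and can only reduce the expected group difference.

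The size is unknown from the document. On the planning values and the assumptions above, two-sided power for craving falls from 0.79 to somewhere between 0.79 (pre-dose scores at a quarter of the later peak) and 0.08–0.14 (pre-dose scores equal to it). The CIWA-Ar part of the outcome has the same structure, but its loss cannot be calculated. This should be fixed; confidence is moderate because the existence, frequency and level of pre-dose ratings are not stated.

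**What to change.** In section 7.a, define the outcome as the peak CIWA-Ar score and the peak craving score from the first dose of study drug to the end of abstinence day 3. In section 4.a, require one CIWA-Ar and one craving score just before the first dose, using the instruments already in use. In section 7.c, name that pre-dose score as the baseline covariate in the ANCOVA already planned.

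The cost is one timed rating on day 1 and a sentence or two of text. No dosing, treatment rule or sample size changes. Anchoring the peak restores the design power (0.79 two-sided, 0.88 one-sided by the t-test) and does not raise it above that. The times of the first dose and of each day-1 rating should be recorded, because the peak cannot be re-anchored later if their order is unknown.

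While editing, reconcile the sequence of conditions, which lists CIWA-Ar under days 1-2, with the outcome window of days 1-3.

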Medical assessment results will be reviewed by [name], the study physician, and persons in whom study participation is contraindicated will be excluded. Psychological and substance use interview results will be reviewed by [name], a licensed psychologist. We typically consent and screen 4 persons for each subject who meets study eligibility criteria. Inclusion and exclusion criteria are detailed in section 5. It is established that cycle phase can influence HPA-axis reactivity to social stress^[71, 72]. In females, cycle phase will be determined via menstrual diary. Ideally, women will be scheduled to complete procedures during their luteal phase. We recognize that heavy drinking can disrupt cycle regularity, and will therefore confirm cycle phase via progesterone level (gold standard), and will include this as a covariate in our analyses.

Subjects will be randomized to treatment groups (OT or placebo), matching for age, gender, and nicotine dependence status (as defined by FNDT score) by Johns Hopkins Investigational Drug Services (IDS). The FNDT score determined at assessment will be used to categorize participants according to nicotine dependence levels as defined by the instrument (Total Score of 0-2 = No Dependence; 3-5 = Moderate Dependence and 6-9 = Substantial Dependence) and provided to IDS for randomization.

Table 1: Assessment instruments:

The Alcohol Use Disorders Identification Test (AUDIT)
MINI for DSM-V
MINI Tobacco Use Disorder
Health Checklist
CIWA-Ar
90-day Time-line Follow-back (TLFB)
Shipley Institute of Living
REALM (if Shipley below score of 18)
Fagerström Nicotine Dependence Test
Spielberger State-Trait Anxiety Inventory (STAI)

Beck Depression Inventory (BDI- II)
Alcohol Dependence Scale (ADS)
Short Profile of Moods State (POMS)
Menstrual Cycle Questionnaire (Females only)

Phosphatidylethanol (PEth). A small blood sample will be collected via finger stick for the BloodSpot® collection test (US Drug Testing Laboratory, Des Plaines, IL). We selected dried blood spot vs. whole blood assays as it reduces subject risk associated with venipuncture and PEth is more stable in dried blood samples than in whole blood^[73, 74]. PEth provides a biomarker for heavy alcohol consumption due to its high specificity and slow degradation rate^[68, 75]. Participants must have a positive PEth (≥ 8 ng/mL) at assessment for study inclusion.

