- iii. *Blood collection:* Blood draw procedures involve minimal risks, such as a slight risk of discomfort at the intravenous site. A small amount of bleeding under the skin will produce a bruise in about 5% of cases. The risk of temporary clotting of the vein is about 1%. The risk of infection or significant blood loss is less than 1 in 1000. In rare cases, fainting could occur. For PEth, a small blood sample will be collected via finger stick for the BloodSpot® collection test (US Drug Testing Laboratory, Des Plaines, IL). We selected dried blood spot vs. whole blood assays as it reduces subject risk associated with venipuncture and PEth is more stable in dried blood samples than in whole blood^[73, 74].
- iv. *Urine Collection:* During the CRU stay, all urine voided during the first 48 hours of the CRU stay is collected. There is no risk associated with urine collection, but subjects may find this inconvenient.
- v. *Medically supervised alcohol withdrawal and monitored abstinence:* Eligible participants will undergo monitored alcohol abstinence and alcohol withdrawal on the CRU. There is a risk of complications (e.g., elevated BP, seizures) during alcohol detoxification; treatment with atenolol and/or lorazepam will be provided if needed, and as detailed below. To reduce risk, applicants with a history of withdrawal-related seizures or other serious alcohol withdrawal symptoms will be excluded from participation. We have been safely using this procedure under IRB approval for over 15 years.
 - a. *Atenolol.* Participants that have elevated blood pressure that are above safe limits (systolic blood pressure >180 and/or diastolic blood pressure >105) will be given atenolol (25 mg BID), which is approved by the Food and Drug Administration for treatment of hypertension. The most common symptoms of atenolol include dizziness, lightheadedness, tiredness, drowsiness, depression, nausea and diarrhea. Less common but more serious side-effects include: shortness of breath, and swelling of the hands, feet, ankles or lower legs.
 - b. *Lorazepam.* Participants that experience serious withdrawal symptoms as determined by CIWA scores ≥ 12 or physician recommendations, will receive 2 mg lorazepam

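### POMS at assessment is measured before randomisation yet listed as a primary and a secondary outcome; as a minor matter, the UFC outcome window should name the two 24-hour collections actually taken

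*Protocol*

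**What the plan says.** **POMS.** The POMS bullet in Protocol 7.a (primary outcomes) covers the total and subscale scores of the short form at two occasions: assessment and the CRU stay. The tension-anxiety bullet in 7.b (secondary outcomes) also includes assessment, together with the TSST and withdrawal. Table 1 in section 4.a, the battery for the in-person assessment, includes "Short Profile of Moods State (POMS". The text just before that table describes randomisation: "The FNDT score determined at assessment will be used to categorize participants according to nicotine dependence levels", and the resulting category goes to the pharmacy service for the allocation. Section 4.b makes assessment visit 1 and the inpatient stay visit 2. The day-by-day list in 4.a starts dosing on day 1 of the stay.

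Section 7.c refers to the outcomes already listed, compares them between oxytocin and placebo by t-test or a non-parametric equivalent, and plans an ANCOVA for each. Gender and mean drinks per week are given as examples of covariates. Assessment POMS is not named.

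**UFC.** Section 7.a has the primary outcome "UFC for abstinence days 1-3". The Design Overview in 4.a says "24-hr urinary free cortisol (UFC) will be collected for the first 48 hours". The day-by-day list places "24-hr collection of urinary free cortisol" under "Days 1 - 2: Monitored alcohol abstinence". The urinary cortisol paragraph of 4.a says "all urine voided per 24-hrs for the first 48 hours is collected", and the risk section (8.a.iv) says "all urine voided during the first 48 hours of the CRU stay is collected".

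**The concern.** A score taken before allocation and before any drug cannot respond to the drug. In a randomised comparison, any arm difference in it is chance. Listed as an outcome, it is either tested as if it could carry an effect or left with no stated role. The Protocol's stated primary objective is to estimate effect size and variance for a larger trial, so its outcome list should hold only quantities that treatment can affect. The same data, already collected, could sharpen the in-stay POMS comparison.

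The UFC point is of a different order. It is the outcome for Hypothesis 1b, and its stated window does not match the specimens that the rest of the Protocol provides. What is at stake is a clear endpoint definition.

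**Working it through.** The Protocol gives no power or detectable difference for POMS or UFC, so there is no stated figure to reproduce.

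**1. Order of events for POMS.** Assessment (visit 1: POMS and the nicotine score) → randomisation using the nicotine score from that visit → admission and first dose (day 1 of visit 2). Assessment POMS therefore precedes both allocation and treatment.

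**2. Size of the chance difference at assessment.** Input: 12 per arm (7.c).
- SD of the difference in means, in SD units: √(2/12) = 0.408.
- P(|difference| > 0.5 SD) = 2 × [1 − Φ(0.5/0.408)] = 2 × [1 − Φ(1.225)] = 0.221.

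This takes simple randomisation. The matching on age, gender and nicotine dependence is ignored and could change it somewhat.

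**3. Detectable difference without the covariate.** Two-sample t-test, 22 df, two-sided 0.05, 80% power, noncentral t with noncentrality d/√(2/12): d = 1.197 SD.

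**4. Detectable difference with assessment POMS as covariate.** ANCOVA, 21 df, with noncentrality d / √[(1 − r²)(2/12)(1 + F/22)], averaged over F ~ F(1, 22) to allow for chance imbalance in the covariate. Here r is the correlation between assessment and in-stay POMS. The Protocol does not give it, so a range is shown. All 24 subjects are taken as analysed.

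| r (assumed) | Detectable d at 80% power | Power at d = 1.197 |
|---|---|---|
| 0 | 1.228 | 0.779 |
| 0.3 | 1.172 | 0.816 |
| 0.5 | 1.064 | 0.883 |
| 0.7 | 0.877 | 0.968 |

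Adjusted and unadjusted analyses break even at r = 0.225. At r = 0 the cost is 1.228 − 1.197 = 0.031 SD.

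**5. UFC window against collection.** Three days read as 24-hour periods would be 3 × 24 = 72 h. Collection lasts 48 h, and 48/24 = 2 daily values. The Design Overview, the urinary cortisol paragraph and 8.a.iv all say 48 hours, and the day list puts the collection under days 1-2. Nowhere is a third 24-hour collection planned.

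**The case against.** **POMS.** The bullets can be read as listing the measurement times of one repeated measure, a baseline and the on-treatment values, perhaps with change from assessment in mind. Section 7.c has an open covariate list and says that other baseline measures will be checked for imbalance, so baseline adjustment is available. Naming a particular covariate is commonly left to the SAP. The gain rests on assumed correlations, and the correlation could be low, because 4.b allows up to 6 months for the whole study.

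Much of this stands. The adjustment is permitted, its absence by name is not itself a fault, and the benefit is uncertain. A reader might infer that the investigators have committed to a separate significance test of pre-randomisation POMS, or that they have excluded baseline adjustment. The text establishes neither. What the objection does not remove is the role assigned: the score stands in two outcome lists, and 7.c compares listed outcomes between arms. The bullets do not mention change from assessment, whereas the heart-rate bullet in 7.a explicitly specifies an increase.

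**UFC.** The phrase may only name the 3-day abstinence phase, as the withdrawal and craving bullet in 7.a does. A 48-hour clock started during day 1 could also run into calendar day 3; no admission hour is given. Both readings are possible. A reader might infer that a third of the intended UFC data will be missing or that the arms will be compared unfairly. The documents do not support that: every description of the procedure gives the same 48 hours for all subjects.

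**Conclusion.** The POMS point holds. A score measured before randomisation and dosing is listed as a primary and a secondary outcome, and it cannot show a treatment effect. This is a misplaced role in the outcome list and implies no bias in the in-stay comparison. Moving the score to the covariate side lowers the detectable difference by about 0.02 SD at r = 0.3, 0.13 SD at r = 0.5 and 0.32 SD at r = 0.7, and costs at most 0.03 SD if the correlation is near zero. These figures assume 12 per arm all analysed, a normal covariate and the stated range of r. They measure the benefit of the change; they are not an error in any power figure of the Protocol.

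The UFC point holds only as a minor wording mismatch. Two 24-hour values are planned under every reading, and no comparison changes.

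**What to change.** - In 7.a and 7.b, delete the assessment time point from the POMS bullets and keep the POMS scores taken after dosing starts as the outcomes.
- In the ANCOVA sentence of 7.c, name assessment POMS as the baseline covariate for the POMS outcomes. Fix this in advance, since the gain depends on a correlation not yet known.
- In 7.a, restate the UFC outcome as UFC from the 0-24 h and 24-48 h collections. Naming one summary, such as their mean, is advisable but may sit in the SAP.
- As a query only: the Protocol does not list the subscales of the short POMS. If tension-anxiety is one of them, it is primary during the CRU stay and secondary during withdrawal, so the authors should say which tier applies.

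The cost is wording in 7.a, 7.b and one sentence of 7.c. No procedure, sample or subject is added.
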